8.3.2 Weeks 52 and 104 – All Participants

The Data Collection Visits at Weeks 52 (\pm 3 months*) and 104 (\pm 14 days) will take place at the study site for all participants in both study groups. Weight, waist circumference, blood pressure and pulse rate will be recorded in line with study SOPs, any AEs/SAEs will be noted, and documentation of inclusion/exclusion criteria and changes in medication and/or diseases will be performed. Blood samples for standard laboratory testing of biochemical outcomes (HbA1c, FBC, U+Es, lipids, LFTs, TFTs, amylase) will be taken and participants will be requested to complete research questionnaires (see Appendix 3). A pregnancy test will take place for all female participants of child-bearing potential (in both standard care and LIRA 3mg targeted prescribing pathway groups).

A urine ACR will be performed for participants with diabetes, prediabetes and hypertension. All participants will complete the Epworth Sleepiness Scale to capture any improvement/decline in daytime sleepiness during the course of the study and the Stop Bang questionnaire to capture any undetected OSA cases, at 3 data collection visits (Baseline, Weeks 52 and 104). OSA patients will be managed through their local sleep clinic as per standard care. Those participants that are patients of the sleep clinic will have their notes reviewed to determine whether or not they are CPAP compliant and thus ‘successful’ against the below criteria.

- a. CPAP usage \geq 4 hrs/night = successful
- b. CPAP usage $<$ 4 hrs/night = struggling
- c. CPAP usage \leq 1 hrs/night = failure

Additional procedures at **Weeks 52 and 104** for the participants in the standard care group who have been prescribed and started anti-obesity medications (for example Orlistat) will be to ascertain whether they are still on the medication, their adherence, and any side effects.

Additional procedures at the **Week 52** visit for all participants who are on **LIRA 3mg** will include:

- Identification of participants on LIRA 3mg who have lost $\geq 15\%$ weight loss and meet the pre-specified criteria to continue on LIRA 3mg. These participants will meet the study clinician in order to be offered LIRA 3mg for another 52 weeks, to receive a new prescription of LIRA 3mg and to discuss adherence with the treatment and any side effects. Pregnancy testing will be undertaken as standard for this visit and clear instructions regarding contraception until the end of the study will be provided

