As a result of conducting virtual consultations and telephone calls, the following procedures will not be performed during the COVID19 pandemic, therefore have been halted as an urgent safety measure:

- BP and Pulse measurements – Participants who are known to have hypertension have home BP monitoring machines and their BP measurements are being collected and assessed by the study team during remote visits. There is no undue risk for those who do not have hypertension, as Liraglutide is not related to BP, and participants are all established on the drug.
- Bloods (lipids, renal, LFTs, thyroid, FBC & HbA1c, amylase) at V9, 11 & 13/15 only - The amylase test usually taken at visits 9, 11 & 15 is a safety blood in relation to pancreatitis. During the remote visits, all participants will be monitored for any new symptoms which will be appropriately managed by the study clinical team. The small number of participants who have diabetes will regularly check their blood glucose at home as usual. All other bloods are taken to assess efficacy, therefore not conducting them will have no impact on participant safety. All participants will be asked to report AE/SAE during remote visits.
- ACR urine test – Not conducting this poses no additional risk to participants.

Once restrictions due to the COVID19 pandemic have been lifted, a further risk assessment will be completed and in agreement with the Sponsor, Study team and NHS Host Organisations, face to face visits will be re-implemented. For the avoidance of doubt, virtual consultations will still be an option for study visits, as preferred by the participant or recommended by the study clinician, to aid the retention of participants and study visit attendance and collection of primary outcome data (via self-reported weight measurement data).

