10.3 Expected Serious Adverse Events/Reactions

Rare side-effects (less than 1%) will be reported as SAEs. The expected adverse events of renal impairment, cholecystitis and cholelithiasis will be reported as SAEs due to being medically significant.

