14.10 Other Ethical Considerations

14.10.1 Known and potential risks

LIRA 3mg is administered as a one daily subcutaneous injection and is available in a prefilled, disposable pen device comprising a pen injector and cartridge. There may be some anxiety and concern to starting treatment using a needle-based device and this will be discussed at length with their clinician. It can be taken at any time of the day and is meal independent. The pros and cons of LIRA 3mg will be explained to each participant during the initial consultation for study consent.

LIRA 3mg has a good tolerability profile; however the most frequently reported adverse effects of LIRA 3mg are gastrointestinal, including nausea, diarrhoea, vomiting, constipation, abdominal pain, and dyspepsia. These gastrointestinal adverse effects may occur more frequently at the start of treatment with LIRA 3mg, and usually diminish within a few days or weeks on continued treatment. Hypoglycaemia is considered low risk with this treatment because its action is glucose dependent. However, participants suffering with diabetes on treatment with sulphonylureas may be at higher risk for hypoglycaemic episodes compared to the other participants.

Rare serious adverse events may include hepatobiliary diseases such as associated with gallstone formation and pancreatitis. An increase incidence of breast malignancies previously reported may be due to reduced adipose tissue in the breast and earlier detection.

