Overall hypoglycaemia rate – ADA definition	52, 104	Hypoglycaemia events will be defined as per Appendix 5 for people without

		diabetes and as per the ADA definition in Appendix 5 for people with diabetes. Hypoglycaemia rate will be calculated per participant as total number of hypoglycaemia events divided by the total follow-up time.
Overall hypoglycaemia rate – Novo Nordisk	52, 104	Hypoglycaemia events will be defined as per Appendix 5 for people without diabetes and as per the Novo Nordisk definition in Appendix 5 for people with diabetes. Hypoglycaemia rate will be calculated per participant as total number of hypoglycaemia events divided by the total follow-up time.
AEs	Continual	Defined as in protocol with MEDRA coding used to classify AEs into System Organ Classes
SAEs	52, 104	Defined as in protocol with MEDRA coding used to classify SAEs into System Organ Classes
Rates of severe hypoglycaemia	52, 104	Calculated per participant as total number of severe hypoglycaemia events divided by the total follow-up time, where severe hypoglycaemia is defined as hypoglycaemic episodes requiring the assistance of another person to actively administer carbohydrate, glucagon, or other resuscitative actions (i.e., 'severe hypoglycaemic episodes')
Change in heart rate from baseline (beats per minute)	52, 104	Follow-up heart rate – baseline heart rate
Compliance of patient with the treatment		
Compliant with Tier 3 service (completers)	52, 104	Binary indicator of 1 if participant is compliant, 0 otherwise (defined in study database)
Stopped treatment with LIRA 3mg because of adverse effects	52, 104	Binary indicator of 1 if participant stopped treatment with LIRA 3mg because of adverse effects*, 0 otherwise. Only defined for participants in intervention arm who were currently eligible for LIRA 3mg treatment. * This includes main reason of 'adverse event' or 'unable to tolerate drug'.
The adherence of participants with the LIRA	52, 104	Participants will be defined as treatment compliant if they self-administer at least 70% of planned doses. Binary indicator of 1 if participant is compliant, 0 otherwise.

3mg (monitored through specific questionnaire and return of used pens)		Given the change in visits as a result of COVID-19 to allow face-to-face, this will be defined using the questionnaire answers as detailed in Appendix 7. Only defined for participants in intervention arm who were currently eligible for LIRA 3mg treatment.

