2.5 Other

There are no other variables to be presented in the statistical report which are not outcomes, baseline or demographic variables, or for measuring compliance or safety.

3 Analysis Sets/Populations

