5.1 Disposition

A CONSORT diagram showing the flow of participants through the study will be produced, including the number of screened and treated participants. This diagram will also show the number of participants receiving the allocated treatment at each stage of the study, along with the reasons for stopping treatment. In particular, the number who stop LIRA 3mg due to each stopping rule will be clearly stated.

The number (percentage) of participants in each analysis population will be tabulated overall and by treatment group. The type and number (percentage) of protocol deviations will also be tabulated overall and by treatment group in the ITT population.

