5.8 Changes to the Planned Analysis

In the protocol, it stated that most secondary outcomes would be subject to formal statistical testing, with some secondary outcomes (safety, treatment compliance, treatment satisfaction) tabulated only, without statistical testing. However, due to the large number of secondary outcomes, it was decided that more secondary outcomes should be tabulated only to reduce the impact of multiple testing. The following outcomes were the ones for which the approach changed: obesity-related comorbidities, referrals to Tier 4 services, and physical activity.

In the protocol, the majority of the secondary outcomes were listed as absolute values, however the change from baseline will instead be analysed for continuous variables.

In the protocol, it states that ACR will be analysed as a secondary outcome for participants with diabetes. However, ACR was also measured for participants with prediabetes or hypertension and so these have been added to the ACR secondary outcome definition.

In the protocol, it was stated that participants who had bariatric surgery would be excluded from the complete cases, per protocol, and responder populations. However, it is more likely that these individuals will be poor responders and so excluding them could potentially bias the analyses. Therefore, participants who had bariatric surgery during the study period will be only be included at time-points prior to their bariatric surgery. They will be excluded from time-points after their bariatric surgery.

In the protocol, it stated that adjusted proportions or means would be presented by treatment group in the primary and secondary analyses. However, the unadjusted raw values are presented instead.

6 Safety and Adverse events (AEs)

The safety outcomes (including AEs and SAEs) will be summarised overall, by randomisation group, and by whether or not the participant was currently receiving LIRA 3mg treatment using count and percentage. The following information will also be presented:

- Incidence rate (per person-year) of each System Organ Class of AEs by treatment and overall
- Proportion of participants with at least one AE, by System Organ Class type, treatment arm, and overall
- Incidence rate (per person-year) of each expected AE type by treatment and overall
- Proportion of participants with at least one expected AE, by AE type, treatment arm, and overall
- Bar chart of number of AEs per individual, split by treatment

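### Renal profile, liver tests and amylase are collected at weeks 32, 52 and 104 but have no planned summary; one descriptive table would close the gap

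*SAP*

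**What the plan says.** Protocol 8.4 (week 32) and 8.3.2 (weeks 52 and 104) take the same blood panel from all participants: HbA1c, full blood count, U+Es, lipids, liver tests, thyroid tests and amylase. Table 1 of the protocol lists the renal profile (with creatinine and eGFR), liver tests and amylase in its Outcomes column.

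Protocol 8.10 says "The amylase test usually taken at visits 9, 11 & 15 is a safety blood in relation to pancreatitis". The same bullet describes the other bloods as taken for efficacy. The safety list in protocol 6.4.2 names gastrointestinal symptoms, hypoglycaemia, AEs and SAEs, heart rate and blood pressure. It names no blood test.

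The protocol does name the related risks. Section 10.3: "The expected adverse events of renal impairment, cholecystitis and cholelithiasis will be reported as SAEs due to being medically significant". Section 14.10.1: "Rare serious adverse events may include hepatobiliary diseases such as associated with gallstone formation and pancreatitis".

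On reporting, SAP section 6 says "The safety outcomes (including AEs and SAEs) will be summarised overall, by randomisation group", and then specifies AE and SAE tables and listings. SAP 2.5 closes the list of reported variables: "There are no other variables to be presented in the statistical report which are not outcomes, baseline or demographic variables". That sentence goes on to allow compliance and safety variables as well, but the safety variables set out in SAP 2.2.1 include no renal, liver or amylase value.

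**The concern.** Safety is secondary objective 7 and the trial is open-label. Whether a moderate fall in eGFR or rise in a liver enzyme becomes an AE is decided by people who know the allocation. Scheduled laboratory values are a second source of evidence, available for renal and liver tests in both randomised arms. As the plan is written, the report would never show them, not even at baseline.

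Timing matters a little. SAP section 1 allows unplanned analyses later, but they must be labelled as such. The SAP pages supplied are marked as a draft, and section 1 allows amendment before database lock, so a table added now would be pre-specified.

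**Working it through.** The plan gives no figure on this point, so the check sets what is collected beside what is reported, then counts who could contribute.

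**1. Collected against reported**

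| Blood-test group (protocol Table 1) | Follow-up draws | Summary in SAP 2.2.1, section 6 or templates 16.3–16.15 |
|---|---|---|
| HbA1c | both arms | yes |
| Lipids | both arms | yes |
| Renal profile with eGFR | both arms | none |
| Liver tests | both arms | none |
| Thyroid tests | both arms | none |
| Full blood count | both arms | none |
| Amylase | unclear, see step 3 | none |

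Two of seven are summarised and five are not. Renal profile, liver tests and amylase are singled out because they bear on risks the protocol names: renal impairment, hepatobiliary disease and pancreatitis.

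**2. Other routes into the report**

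- AE or SAE: protocol 10.1.1 allows an abnormal laboratory finding to be an AE, and 10.3 requires three diagnoses to be reported as SAEs. Neither document gives a numeric follow-up threshold for eGFR, liver tests or amylase.
- Stopping drug: SAP 2.2.1 has the endpoint "Stopped treatment with LIRA 3mg because of adverse effects", and SAP 5.1 has the CONSORT diagram show numbers on treatment "along with the reasons for stopping treatment". Protocol 8.8.3 leaves a laboratory-led stop to clinician opinion and a recheck, with thresholds still to be defined with the sponsor's representative.
- Urine ACR is the only kidney marker summarised, and only for participants with diabetes, prediabetes or hypertension.

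The first two routes show events that someone chose to record, not laboratory values.

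**3. Who could contribute**

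*Renal and liver, week 52.* With 261 and 131 randomised and the plan's 25% dropout: 261 × 0.75 = 195.75 and 131 × 0.75 = 98.25, about 196 v 98. The documents do not say how many bloods COVID-19 cost. If a further 25% were missing (assumption), 147 v 74; if 50%, 98 v 49. The documents give no week-104 dropout. The amendment history puts the end of recruitment at 29/02/2020. If recruitment ran the full 24 months of protocol 7.1 (assumption), week-104 visits ran from about March 2020 to February 2022, so that visit is the most exposed.

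*Amylase.* The text of 8.3.2 and 8.4 takes it from everyone. Appendix 3 stars it as only for liraglutide participants on active treatment, and 8.10 cites visit 15, which is the liraglutide-arm number for week 104. It was probably limited to participants on drug.

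- Week 32 (passed the week-16 rule): protocol section 4 gives ≥15% loss in 24.2% of early responders and 1.8% of early non-responders. For an overall rate r, the responder share is (r − 1.8)/(24.2 − 1.8). At r = 14%: 12.2/22.4 = 54.5%, and 261 × 0.545 = 142. At the plan's 16%: 14.2/22.4 = 63.4%, and 261 × 0.634 = 165. After 25% dropout: 107 to 124.
- Week 104 (passed the week-52 rule): 0.16 × 261 = 42; after 25% dropout, 0.16 × 195.75 = 31.
- Week 52 lies between these.

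The 165 and 42 are upper bounds at a 16% response, before dropout and intolerance. The 42 also counts everyone with ≥15% loss as still on drug and tested a year later. At 20%, the top of the plan's likely range, the same arithmetic gives 18.2/22.4 × 261 = 212 and 0.20 × 261 = 52.

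**4. Who has a value at all**

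Protocol 8.10 halts these bloods at visits 9, 11 and 13/15 during the pandemic. It then keeps virtual visits available by participant preference or clinician recommendation. Both parties know the allocation, so missing values are partly selective.

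**The case against.** The strongest reply is that nothing is broken. Protocol 6.4.2 lists no blood test under safety, the SAP covers every safety outcome named there, and 8.10 says the non-amylase bloods serve efficacy and that omitting them does not affect participant safety. The one test it calls a safety blood probably has no controls. Renal impairment and gallbladder events must be reported as SAEs. Laboratory values that might stop treatment are rechecked. AEs and SAEs are tabulated by arm with rate ratios and fully listed. An independent DSMC reviewed safety during the trial. Entry requires diabetes, prediabetes, hypertension or sleep apnoea, so ACR is planned for all but those with sleep apnoea alone. The trial is Phase IV with a licensed drug.

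Most of this stands, and it fixes the grade. It does not remove the gap. If renal and liver tests are efficacy bloods, the SAP still summarises them under neither heading. The DSMC input that protocol 16.3 names is a log of AEs, the same judgement-based source. AE tables go below System Organ Class only for classes above 0.1 AEs per person-year, apart from the listed expected AE types, so an infrequent hepatic or renal event outside those types may be visible only in listings. ACR does not replace eGFR, and it too was halted during the pandemic.

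**Conclusion.** A minor point: a cheap improvement to safety reporting, not an error. Renal, liver and amylase results are collected and, as the plan is written, never summarised. The primary result and the listed outcomes do not change.

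Three stronger inferences are not supported:

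- *That the SAP dropped a protocol safety outcome.* It did not. Table 1 lists these tests as collected variables, but 6.4.2 does not name them as safety outcomes.
- *That laboratory harm would go unseen.* AE, SAE, stopping and DSMC routes exist; they cover it in part.
- *That the laboratory values would give a comparison free of allocation knowledge.* They would not, because who has a value depended partly on virtual visits chosen by participants or clinicians. The comparison is supportive only.

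The conclusion itself rests on reading the two documents side by side. The numbers rest on the plan's 25% dropout and 16% response, on assumed COVID-19 losses, and, for week-32 amylase, on responder rates from a cited trial applying here.

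**What to change.** Add to SAP section 6 and Appendix 9 one descriptive laboratory table in the safety population, by arm, at weeks 32, 52 and 104, with the screening value as baseline:

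- N with data and N missing by arm and visit, separating bloods not taken because of COVID-19 or a virtual visit.
- eGFR: change from baseline, and the count at or below 30 ml/min/1.73m², the trial's own exclusion limit.
- ALT, ALP and bilirubin: change from baseline, and counts above the local upper limit where captured.
- Amylase: counts above the upper limit and above three times it (the exclusion limit). If controls were not tested, show on-liraglutide participants only, with no between-arm contrast.
- A note that values are selectively missing, so the comparison is supportive.

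If section 6's split by current liraglutide use is applied here too, label it non-randomised, because continuation depends on weight loss. No tests, p-values or intervals are needed. Thyroid tests and full blood count could be added but are not requested.

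The cost is one table and a check of which laboratory fields and local limits the database holds. N will be reduced, and where upper limits were not recorded the liver tests can show only change from baseline.

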9.4 Compliance with Study Treatment

All participants in the study who have been prescribed LIRA 3mg should administer the drug daily. The participants will be instructed to return all unused, used or part-used medication/vials and packaging from used medication at each visit. Adherence questions will also be asked in follow-up visits for participants on LIRA 3mg. Examining medication returns and evaluating adherence will allow for an assessment of compliance and drug accountability. All participants should report all events which they believe may have impact on dose adjustment (such as nausea, vomiting). The Investigator may withdraw the participants if they consider dose compliance is unsatisfactory. Participants will be defined as treatment compliant if they take 70% of planned doses.

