11.5 Analysis Populations

Complete cases population

The complete cases population is defined as all randomised participants who have data available for the outcome being analysed, according to the study group to which they were randomised at baseline. Participants who had bariatric surgery during the study period will be excluded from this population.

ITT population

The ITT population are all randomised participants and they will be analysed according to the treatment group to which they were randomised at baseline. Missing outcome data will be imputed. Participants who had bariatric surgery during the study period will be included in this population.

Per protocol population

The per protocol population is defined as all participants who were compliant with their randomised treatment group, analysed according to the treatment group to which they have randomised at baseline. Participants in the standard care group are defined as treatment compliant if they complete at least 70% of the planned contacts in the Tier 3 service. Participants in the intervention group are defined as treatment compliant if they complete at least 70% of the planned contacts in the Tier 3 service, and take at least 70% of their planned doses of LIRA 3mg as stipulated by the prescribing pathway. Participants who had bariatric surgery during the study period will be excluded from this population.

Responder population

The Responder population is defined as all participants in the intervention group who achieved $\geq 15\%$ weight loss at 52 weeks, and all participants in the standard care group. Participants will be analysed according to the treatment group to which they were randomised at baseline. Participants who had bariatric surgery during the study period will be excluded from this population.

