Total Leisure-Time MET-minutes/week = sum of Walking + Moderate + Vigorous MET-minutes/week scores in leisure.

Total Scores for all Walking, Moderate and Vigorous Physical Activities

Total Walking MET-minutes/week = Walking MET-minutes/week (at Work + for Transport + in Leisure)

Total Moderate MET-minutes/week total = Moderate MET-minutes/week (at Work + Yard chores + inside chores + in Leisure time) + Cycling Met-minutes/week for Transport + Vigorous Yard chores MET-minutes/week

Total Vigorous MET-minutes/week = Vigorous MET-minutes/week (at Work + in Leisure)

Note: Cycling MET value and Vigorous garden/yard work MET value fall within the coding range of moderate-intensity activities.

Total Physical Activity Scores

An overall total physical activity MET-minutes/week score can be computed as: Total physical activity MET-minutes/week = sum of Total (Walking + Moderate + Vigorous) METminutes/week scores.

This is equivalent to computing: Total physical activity MET-minutes/week = sum of Total Work + Total Transport + Total Domestic and Garden + Total Leisure-Time MET-minutes/week scores.

As there are no established thresholds for presenting MET-minutes, the IPAQ Research Committee proposes that these data are reported as comparisons of median values and interquartile ranges for different populations.

14 Appendix 7 Definitions for adherence of participants with the LIRA 3mg

Individuals that didn't receive 70% of the doses as determined by the protocol (i.e. in the first 16 weeks or there after whilst continuing to meet the continue rules of the protocolised treatment schedule) will be classed as not adhering with the LIRA 3mg pathway.

Defining days taking LIRA

The number of days taking LIRA will be calculated as the time from first dose dispensed (normally at baseline visit) to the last known date of individuals taking the LIRA. Where individuals are recorded as not completing the trial due to stopping the LIRA, the date of last dose of LIRA in the completion form will be used; if this is not recorded then the date of first visit at which individuals say they are not happy to continue taking LIRA will be used; and where neither of these are recorded the date of the last visit that individuals said they are happy to continue LIRA will be used.

14.1 52 weeks

Individuals will then be assessed for whether they have received 70% as per table below.

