Stopping rule on protocolised treatment schedule	Did not receive 70% of planned doses	Did receive 70% of planned doses
Did not meet rule to continue on Lira at 16 weeks (either <5% weight loss or not measured)	If days taking LIRA is <70% of days between baseline and Week 16. Or, if Week 16 date missing, if days taking LIRA is ≤ 78 .	If days taking LIRA is $\geq 70\%$ of days between baseline and Week 16. Or, if Week 16 date missing, if days taking LIRA is >78
Did meet rule to continue Lira ($\geq 5\%$ weight loss) at 16 weeks but did not meet rule to continue Lira at 32 weeks (either <10% weight loss or not measured)	If days taking LIRA is <70% of days between baseline and Week 32. Or, if Week 32 date missing, if days taking LIRA is ≤ 156 .	If days taking LIRA is $\geq 70\%$ of days between baseline and Week 32. Or, if Week 32 date missing, if days taking LIRA is >156 .
Did meet rule to continue Lira ($\geq 5\%$ weight loss) at 16 weeks and did not meet rule to continue Lira at 32 weeks ($\geq 10\%$ weight loss)	If days taking LIRA is <70% of days between baseline and week 52. Or, if week 52 date missing, if days taking LIRA is ≤ 254 .	If days taking LIRA is $\geq 70\%$ of days between baseline and week 52. Or, if week 52 date is missing, if days taking LIRA is >254 .

14.2 104 weeks

Individuals will then be assessed for whether they have received 70% as per table below.

Stopping rule on protocolised treatment schedule	Did not receive 70% of planned doses	Did receive 70% of planned doses
Did not meet rule to continue on Lira at 16 weeks (either <5% weight loss or not measured)	If days taking LIRA is <70% of days between baseline and Week 16. Or, if Week 16 date missing, if days taking LIRA is ≤ 78 .	If days taking LIRA is $\geq 70\%$ of days between baseline and Week 16. Or, if Week 16 date missing, if days taking LIRA is >78
Did meet rule to continue Lira ($\geq 5\%$ weight loss) at 16 weeks but did not meet rule to continue Lira at 32 weeks (either <10% weight loss or not measured)	If days taking LIRA is <70% of days between baseline and Week 32. Or, if Week 32 date missing, if days taking LIRA is ≤ 156 .	If days taking LIRA is $\geq 70\%$ of days between baseline and Week 32. Or, if Week 32 date missing, if days taking LIRA is >156 .

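### SAP Appendix 7 measures time from first dispensing to last known use of LIRA 3mg, but labels the result as receipt of 70% of planned doses

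*SAP*

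**What the plan says.** Protocol section 9.4 sets a dose criterion: "Participants will be defined as treatment compliant if they take 70% of planned doses". Dosing is daily, and compliance is to be judged from returned medication and adherence questions. Protocol section 11.5 carries the criterion into the per-protocol population: besides attending 70% of Tier 3 contacts, intervention participants must "take at least 70% of their planned doses of LIRA 3mg as stipulated by the prescribing pathway". SAP sections 2.4 and 3.3.3 reproduce that text.

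For the adherence endpoint, SAP section 2.2.1 says: "Participants will be defined as treatment compliant if they self-administer at least 70% of planned doses". It adds that, because visits changed during COVID-19, "this will be defined using the questionnaire answers as detailed in Appendix 7". Section 3.3.3 sends the dose part of the per-protocol definition to the same appendix.

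Appendix 7 then says: "The number of days taking LIRA will be calculated as the time from first dose dispensed (normally at baseline visit) to the last known date" on which LIRA was used. For people recorded as not completing the trial because they stopped LIRA, the end date is the last-dose date on the completion form. Failing that, "the date of first visit at which individuals say they are not happy to continue taking LIRA will be used"; failing that, "the date of the last visit that individuals said they are happy to continue LIRA will be used". Tables 14.1 and 14.2 compare the span with the days from baseline to the relevant decision visit, for example: "If days taking LIRA is <70% of days between baseline and Week 16". If the visit date is missing, whole-day cuts of 78, 156, 254 and 510 apply at weeks 16, 32, 52 and 104. The column headings state that 70% of planned doses was or was not received.

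Protocol section 8.8.5 permits temporary discontinuation and asks sites to record how long it lasts. SAP section 5.8 lists five departures from the protocol; none concerns adherence.

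**The concern.** A span from first dispensing to last use equals a dose count only if every daily dose inside it was taken. The protocol does not assume this: it foresees interruptions and plans to examine medication returns. Appendix 7 uses neither interruption lengths nor pen counts. Participants who took fewer than 70% of their doses can therefore enter the per-protocol set and be counted as compliant.

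Three results depend on the rule: the per-protocol secondary analysis of the primary outcome (SAP 5.4.2), the exploratory analysis built on the same set (5.4.4), and the LIRA adherence endpoint (2.2.1, table 16.14). A reader who has the definition in protocol 11.5 or SAP 2.4 would take all three to rest on doses taken.

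**Working it through.** **Inputs.** One planned dose per day (protocol 9.4). Decision visits at weeks 16, 32 and 52 and the final visit at week 104, so nominal periods of 112, 224, 364 and 728 days. Threshold 70%. Interruption lengths and intake patterns below are assumptions, because the documents give none.

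**Step 1: reproduce the cuts (0.7 × days).**
- Week 16: 0.7 × 112 = 78.4; the SAP uses ≤78.
- Week 32: 0.7 × 224 = 156.8; the SAP uses ≤156.
- Week 52: 0.7 × 364 = 254.8; the SAP uses ≤254.
- Week 104: 0.7 × 728 = 509.6; the SAP uses ≤510.

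The cuts are 70% of calendar days, which confirms that the rule measures time. The first three match the rule. The fourth is one day too high: 510/728 = 70.05% is classed as below 70%, whereas 509/728 = 69.92% is the last day that belongs there.

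**Step 2: missed days that the rule does not see.** A participant who misses days but is on the drug at the decision visit scores about 100%. The smallest number of missed days that brings doses taken below 70% is:
- before week 16: 34 days, (112 − 34)/112 = 78/112 = 69.6% (33 days gives 79/112 = 70.5%);
- before week 32: 68 days, (224 − 68)/224 = 156/224 = 69.6% (67 days gives 157/224 = 70.1%);
- before week 52: 110 days, (364 − 110)/364 = 254/364 = 69.8% (109 days gives 255/364 = 70.05%).

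Scattered misses behave in the same way. Three missed doses a week gives 4/7 = 57.1%, and alternate-day use to week 52 gives 182/364 = 50%. Both score 100%.

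**Step 3: the end date.** Appendix 7 attaches its three sources to people recorded as not completing the trial because they stopped LIRA. Protocol 8.8.4 keeps people who stop LIRA under observation, so many of them may not be recorded that way. For them the text gives only the general rule of last known use. *If* the two visit-date fallbacks are applied to them, errors can run both ways:
- Too long: a participant meets the week-16 target, stops on day 113, skips week 20 (optional under protocol 8.4), first says so at week 32 and has not reached 10% weight loss. Scored 224/224 = 100%; actual 113/224 = 50.4%.
- Too short: a participant last seen at week 16, when the week-16 target was met, uses LIRA to day 200 and misses week 32. Credited 112 days, which is ≤156 and so below 70%; actual 200/224 = 89.3%.

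**Step 4: table 14.1, row 3.** The row says that the week-32 rule was not met, but its bracket gives at least 10% weight loss, its denominator runs to week 52, and the matching row of table 14.2 says the rule was met. Read in context it misclassifies nobody.

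**The case against.** The strongest reply is that the proxy is disclosed. SAP 2.2.1 explains the move to questionnaire answers, 3.3.3 points to Appendix 7, and Appendix 7 states the formula. With once-daily dosing, days on drug are a natural stand-in, and protocol 6.4.2 allows days taking the drug as one way of costing it. This shows that the measure is open and defensible as a proxy. It does not make it a dose count: the COVID-19 note explains a new data source, not a change from doses to elapsed time, and 5.8 is silent.

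Four narrower objections stand.
- A reader might infer from Step 3 that people who stop LIRA but stay in follow-up always get a visit date. The text does not say so. The governing rule is last known use, and protocol 8.8.4 has permanent discontinuations recorded in the CRF, so a better date may exist. Someone not happy to continue may also still be injecting at that visit. The defect is ambiguity; the two examples are conditional.
- The documents do not say whether days of an interruption directed by the investigator count as planned doses. The interruption examples depend on counting them; the scattered-miss examples do not.
- The dose wording in SAP 2.4 and the opening of 3.3.3 is copied from the protocol, so it should be annotated and not rewritten.
- The results templates do not repeat the 70% dose wording: table 16.7 says per protocol and table 16.14 says compliant. The mislabel sits in the definitions and the Appendix 7 headings.

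**Conclusion.** The point holds and should be fixed before the SAP is signed off. Appendix 7 measures time to last known use, and as written it can class a participant with fewer than 70% of doses as having received 70%. The departure from the protocol's dose definition is missing from SAP 5.8, and the end-date rule is ambiguous for people who stop LIRA but remain under observation.

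The reach is limited to the three results named above. Table 14.2 matters only for the descriptive 104-week adherence row, because SAP 5.5.1 analyses secondary outcomes in complete cases only. The 510-day cut matters only for a participant with exactly 510 days and no week-104 date.

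A reader might infer that the main efficacy result is compromised, or that the per-protocol odds ratio is biased in a known direction. The documents support neither. The complete-cases primary analysis and the ITT analysis do not use Appendix 7. Without intake or interruption data, the number of people misclassified and the size and direction of any effect cannot be derived. Such cases may be uncommon, since protocol 9.2 withdraws people who do not tolerate the drug from treatment and 9.4 allows withdrawal for poor compliance.

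**What to change.** 1. In SAP 5.8, list the change from doses taken to time on treatment. In 2.2.1, the Appendix 7 column headings and table 16.14, describe the measure as *time from first dispensing to last known use of at least 70% of the planned treatment period*. Add a note beside the protocol text in 2.4 and 3.3.3, leaving that text as it is. Cost: wording only.
2. Where interruption durations are in the database, subtract them from the days taking LIRA, keep the denominator, and call the result *days on treatment net of recorded interruptions*. State that scattered missed doses are not counted. Cost: a short derivation, possible only if the durations were captured, which the documents do not confirm. Downside: the records may be incomplete, and participants whose interruption was directed by the investigator may be classed as below 70%.
3. For people who stop LIRA but remain in follow-up, use a recorded stop date where there is one before any visit date. Report how many participants were classified from each end-date source. Cost: one sentence and one table row per source.
4. Change the week-104 fallback from ≤510/>510 to ≤509/>509.
5. Editorial: in row 3 of table 14.1, state that the week-32 rule to continue was met, matching table 14.2.

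Items 4 and 5 are text corrections. The SAP is marked as a draft and is to be signed off before database lock, so all five can be made in the normal course.
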